11.1.3 Expectedness

Adverse events can be 'Expected' or 'Unexpected.'

11.1.3.1 Expected adverse event

Expected adverse events are those that have been previously identified as resulting from administration of the agent. For the purposes of this study, an adverse event is considered expected when it appears in the current adverse event list, the Investigator's Brochure, the package insert or is included in the informed consent document as a potential risk.

Refer to Section 6.1 for a listing of the most common expected adverse events associated with the study agent(s).

11.1.3.2 Unexpected adverse event

For the purposes of this study, an adverse event is considered unexpected when it varies in nature, intensity or frequency from information provided in the current adverse event list, the Investigator's Brochure, the package insert or when it is not included in the informed consent document as a potential risk.

11.1.4 Attribution

Attribution is the relationship between an adverse event or serious adverse event and the study treatment. Attribution will be assigned as follows:

- Definite – The AE is clearly related to the study treatment.
- Probable – The AE is likely related to the study treatment.
- Possible – The AE may be related to the study treatment.
- Unlikely - The AE is doubtfully related to the study treatment.
- Unrelated - The AE is clearly NOT related to the study treatment.

11.2 Procedures for AE and SAE Recording and Reporting

Participating investigators will assess the occurrence of AEs and SAEs at all participant evaluation time points during the study.

CONFIDENTIAL

This document is confidential. Do not disclose or use except as authorized.

All AEs and SAEs whether reported by the participant, discovered during questioning, directly observed, or detected by physical examination, laboratory test or other means, will be recorded in the participant's medical record and on the appropriate study-specific case report forms.

The descriptions and grading scales found in the revised NCI Common Terminology Criteria for Adverse Events (CTCAE) version 4.0 will be utilized for AE reporting, with the exception of hematologic toxicity, which will be graded according to Appendix C. All appropriate treatment areas should have access to a copy of the CTCAE version 4.0.

A copy of the CTCAE version 4.0 can be downloaded from the CTEP website at:

http://ctep.cancer.gov/protocolDevelopment/electronic_applications/ctc.htm.

11.3 Reporting Requirements

For multi-site trials where a DF/HCC investigator is serving as the principal investigator, each participating investigator is required to abide by the reporting requirements set by the DF/HCC. The study must be conducted in compliance with FDA regulations, local safety reporting requirements, and reporting requirements of the principal investigator.

Each investigative site will be responsible to report SAEs that occur at that institution to their respective IRB. It is the responsibility of each participating investigator to report serious adverse events to the overall PI [name] and to Novartis and to Gilead as described below.

11.4 Reporting to the Study Sponsor

11.4.1 Serious Adverse Event Reporting to DF/HCC

All serious adverse events that occur after the initial dose of study treatment, during treatment, or within 6 months of the last dose of treatment must be reported to the DF/HCC Overall Principal Investigator on a MedWatch form. This includes events meeting the criteria outlined in Section 11.1.2, as well as the following:

- Grade 2 (moderate) and Grade 3 (severe) Events – Only events that are unexpected and possibly, probably or definitely related/associated with the intervention.
- Grade 4 (life-threatening or disabling) Events – Unless expected AND specifically listed in the protocol as not requiring reporting. See Section 11.1.2 for grade 4 hematological toxicities.
- All Grade 5 (fatal) Events – When the participant is enrolled and actively participating in the trial OR when the event occurs within 30 days of the last study intervention.

Note: If the participant is in long term follow up, report the death at the time of continuing review.

CONFIDENTIAL

This document is confidential. Do not disclose or use except as authorized.

Participating investigators must report each serious adverse event to the DF/HCC Overall Principal Investigator [name] within 1 business day of learning of the occurrence. In the event that the participating investigator does not become aware of the serious adverse event immediately (e.g., participant sought treatment elsewhere), the participating investigator is to report the event within 1 business day after learning of it and document the time of his or her first awareness of the adverse event. Report serious adverse events by email to investigator, Project Manager, and study coordinator (contact information on study contact list):

PI: [name], PhD
Email: [contact]

Within the following 1-2 business days, the participating investigator must provide follow-up information on the serious adverse event. Follow-up information should describe whether the event has resolved or continues, if and how the event was treated, and whether the participant will continue or discontinue study participation.

11.4.2 Reporting to Gilead

In addition to reporting SAEs to the overall principal investigator, SAEs also must be reported to Gilead as follows:

Serious	Within 15 calendar days	Fax or email relevant CRFs (eg, adverse event form, medical history form, concomitant drug/therapy form) and source documents ^b (eg, progress notes, nurses' notes, laboratory and diagnostic test results, discharge summaries) to Gilead Sciences, Inc. ^a
----------------	-------------------------	---

a. The Gilead fax number is [contact] and email address is [contact]. All documents sent to Gilead should have their internal study number included. Gilead internal study number: IN-US-312-1237.

b. Patient name, address, and other personal identifiers should be obscured.

Abbreviations: CRF, case report form; IRB/IEC, Institutional Review Board/Independent Ethics Committee

All SAEs which are reported to Gilead a copy of the report must also be reported to the overall principal investigator, Project Manager and study coordinator (contact information on study contact list):

PI: [name] PhD,
Email: [contact]

Gilead SAE reporting criteria: See definition of SAE in 11.1.2

All SAEs regardless of relationship to investigational product will be collected from the first dose of investigational product up to 1 month after the last dose of investigational product. SAEs are no longer required to be reported if a subject begins treatment with another therapy.

From the time a subject consents to participate in and completes the study all SAEs assessed **as related to study participation** (e.g., protocol-mandated procedures, invasive tests, or change in existing therapy), will be reported promptly to Gilead.

CONFIDENTIAL

This document is confidential. Do not disclose or use except as authorized.

Any SAE brought to the investigator's attention after the subject has completed the study and considered by the investigator as possibly related to investigational product must be reported to Gilead.

11.4.3 Reporting to Novartis

All Serious Adverse Events including life-threatening events resulting in required hospitalization, disability, congenital anomaly, death, or progression of the disease being greater than expected. In the event that the investigator identifies an SAE according to protocol definitions, the SAE will be reported to Novartis within 24 hours of identification of the SAE. SAEs should be reported to Novartis by fax to: U.S. Drug Safety & Epidemiology at [contact]. . Please use the Novartis SAE Report Fax Coversheet and reference to the Novartis study code provided by the DFCI study team.

All SAEs which are reported to Novartis a copy of the report must also be reported to the overall principal investigator, Project Manager and study coordinator (contact information on study contact list):

PI: [name] PhD,
Email: [contact]

11.4.4 Non-Serious Adverse Event Reporting to DF/HCC

Non-serious adverse events will be reported to the DF/HCC Overall Principal Investigator on the toxicity Case Report Forms.

11.5 Reporting to the Institutional Review Board (IRB)

Investigative sites within DF/HCC will report all serious adverse events directly to the DFCI Office for Human Research Studies (OHRS). Other investigative sites should report serious adverse events to their respective IRB according to the local IRB's policies and procedures in reporting adverse events. A copy of the submitted institutional SAE form should be forwarded to:

[name]
[contact]
[contact]
Email [contact]

The DF/HCC Principal Investigator [name] will submit SAE reports from outside institutions to the DFCI Office for Human Research Studies (OHRS) according to DFCI IRB policies and procedures in reporting adverse events.

11.6 Reporting to the Food and Drug Administration (FDA)

CONFIDENTIAL

This document is confidential. Do not disclose or use except as authorized.

The Overall PI, as study sponsor, will be responsible for all communications with the FDA. The Overall PI will report to the FDA, regardless of the site of occurrence, any serious adverse event that meets the FDA's criteria for expedited reporting following the reporting requirements and timelines set by the FDA. Please refer to appendix E for FDA reporting guidelines.

11.7 Reporting to Hospital Risk Management

Participating investigators will report to their local Risk Management office any subject safety reports or sentinel events that require reporting according to institutional policy.

11.8 Monitoring of Adverse Events and Period of Observation

All adverse events that are encountered from initiation of study intervention, throughout the study, and within 30 days of the last study intervention should be followed to their resolution, or until the participating investigator assesses them as stable, or the participating investigator determines the event to be irreversible, or the participant is lost to follow-up. SAEs and death should be reported for 6 months after the last day of study intervention. The presence and resolution of AEs and SAEs (with dates) should be documented on the appropriate case report form and recorded in the participant's medical record to facilitate source data verification. For some SAEs, the study sponsor or designee may follow-up by telephone, fax, and/or monitoring visit to obtain additional case details deemed necessary to appropriately evaluate the SAE report (e.g., hospital discharge summary, consultant report, or autopsy report).

Participants should be instructed to report any serious post-study event(s) that might reasonably be related to participation in this study. Participating investigators should notify the DF/HCC Overall Principal Investigator and their respective IRB of any unanticipated death or adverse event occurring after a participant has discontinued or terminated study participation that may reasonably be related to the study.

12. DATA AND SAFETY MONITORING

12.1 Data Reporting

12.1.1 Method

The QACT will collect, manage, and perform quality checks on the data for this study.

12.1.2 Data Submission

The schedule for completion and submission of case report forms (paper or electronic) to the QACT is as follows:

Form	Submission Timeline
-------------	----------------------------

CONFIDENTIAL

This document is confidential. Do not disclose or use except as authorized.

Eligibility Checklist	Complete prior to registration with QACT
On Study Form	Within 14 days of registration
Baseline Assessment Form	Within 14 days of registration
Treatment Form	Within 10 days of the last day of the cycle
Adverse Event Report Form	Within 10 days of the last day of the cycle
Response Assessment Form	Within 10 days of the completion of the cycle required for response evaluation
Off Treatment/Off Study Form	Within 14 days of completing treatment or being taken off study for any reason
Follow up/Survival Form	Within 14 days of the protocol defined follow up visit date or call

12.2 Safety Meetings

The DF/HCC Data and Safety Monitoring Committee (DSMC) will review and monitor toxicity and accrual data from this trial. The committee is composed of clinical specialists with experience in oncology and who have no direct relationship with the study. Information that raises any questions about participant safety will be addressed with the Principal Investigator and study team.

The DSMC will review each protocol up to four times a year or more often if required to review toxicity and accrual data. Information to be provided to the committee may include: up-to-date participant accrual; current dose level information; DLT information; all grade 2 or higher unexpected adverse events that have been reported; summary of all deaths occurring within 30 days; any response information; audit results, and a summary provided by the study team. Other information (e.g. scans, laboratory values) will be provided upon request.

12.3 Monitoring

Involvement in this study as a participating investigator implies acceptance of potential audits or inspections, including source data verification, by representatives designated by the DF/HCC Overall Principal Investigator (or Protocol Chair) or DF/HCC. The purpose of these audits or inspections is to examine study-related activities and documents to determine whether these activities were conducted and data were recorded, analyzed, and accurately reported in accordance with the protocol, institutional policy, Good Clinical Practice (GCP), and any applicable regulatory requirements.

All data will be monitored for timeliness of submission, completeness, and adherence to protocol requirements. Monitoring will begin at the time of participant registration and will continue during protocol performance and completion.

CONFIDENTIAL

This document is confidential. Do not disclose or use except as authorized.

13. REGULATORY CONSIDERATIONS

13.1 Protocol Review and Amendments

This protocol, the proposed informed consent and all forms of participant information related to the study (e.g., advertisements used to recruit participants) and any other necessary documents must be submitted, reviewed and approved by a properly constituted IRB governing each study location.

Any changes made to the protocol must be submitted as amendments and must be approved by the IRB prior to implementation. Any changes in study conduct must be reported to the IRB. The DF/HCC Overall Principal Investigator (or Protocol Chair) will disseminate protocol amendment information to all participating investigators.

All decisions of the IRB concerning the conduct of the study must be made in writing.

13.2 Informed Consent

All participants must be provided a consent form describing this study and providing sufficient information for participants to make an informed decision about their participation in this study. The formal consent of a participant, using the IRB approved consent form, must be obtained before the participant is involved in any study-related procedure. The consent form must be signed and dated by the participant or the participant's legally authorized representative, and by the person obtaining the consent. The participant must be given a copy of the signed and dated consent document. The original signed copy of the consent document must be retained in the medical record or research file.

13.3 Study Documentation

The investigator must prepare and maintain adequate and accurate case histories designed to record all observations and other data pertinent to the study for each research participant. This information enables the study to be fully documented and the study data to be subsequently verified.

Original source documents supporting entries in the case report forms include but are not limited to hospital records, clinical charts, laboratory and pharmacy records, recorded data from automated instruments, microfiches, photographic negatives, microfilm or magnetic media, and/or x-rays.

13.4 Records Retention

All study-related documents must be retained for the maximum period required by applicable federal regulations and guidelines or institutional policies.

CONFIDENTIAL

This document is confidential. Do not disclose or use except as authorized.

13.5 Multi-center Guidelines

This protocol will adhere to the policies and requirements of the Dana-Farber/Harvard Cancer Center. The specific responsibilities of the DF/HCC Overall Principal Investigator (or Protocol Chair), Coordinating Center, and Participating Institutions are presented in the Dana-Farber/Harvard Cancer Center Multi-Center Data and Safety Monitoring Plan (see Appendix D).

- The DF/HCC Overall Principal Investigator/Coordinating Center is responsible for distributing all IND Action Letters or Safety Reports to all participating institutions for submission to their individual IRBs for action as required.
- Mechanisms will be in place to ensure quality assurance, protocol compliance, and adverse event reporting at each site.
- Except in very unusual circumstances, each participating institution will order the agent(s) directly from the supplier. A participating site may order the agent(s) only after the initial IRB approval for the site has been forwarded to the Coordinating Center.

14. STATISTICAL CONSIDERATIONS

14.1 Sample Size/Accrual Rate

Primary Objective:

The primary objective for this phase II study is to estimate the overall response rate or ORR (CR+PR) of ofatumumab and idelalisib in previously untreated CLL/SLL.

Hypothesis:

Null: 0.55 ORR

Alternative: 0.75 ORR

Sample size and power calculation:

A two stage design is used to compute the sample size. A total number of 50 eligible patients is needed in order to detect a 75% response rate, assuming the ORR for the null hypothesis is 55%, with 90% power and 4% type I error. 31 patients will be enrolled initially into the study. The study will stop early if only 17 or fewer responses out of 31 patients are observed and the drug will not be declared promising if less than 34 responses are seen in the total 50 patients. The probability of stopping at the first stage is 0.56 if the null hypothesis is true. For the purposes of the two-stage design and in order to avoid potential closure to enrollment, we will use the four month response evaluation to decide about moving to the second stage.

Primary Analysis:

The overall response rate and a 90% confidence interval will also be calculated, using the

CONFIDENTIAL

This document is confidential. Do not disclose or use except as authorized.

method of Atkinson and Brown for a two stage study. Patients' baseline characteristics will be summarized using descriptive statistics (median, interquartile range, proportions).

Enrollment was discontinued at 27 patients and ORR will be estimated based on the data, with 90% confidence interval.

14.2 Analysis of Secondary Endpoints

Other Secondary Objectives:

- To determine the CR rate and PFS of ofatumumab and idelalisib.
- To determine the ORR, CR and rate of nodal PR with lymphocytosis for idelalisib given alone for 2 months.
- To assess the safety of ofatumumab and idelalisib in combination.
- To determine whether clinical response correlates with known CLL molecular prognostic factors.
- To determine whether the use of CT scans in response assessment improves the predictive power of ORR for progression-free or overall survival.
- To determine whether serum ofatumumab levels in vivo predict response.
- To assess whether idelalisib alters the flow cytometric phenotype of circulating CLL cells.
- To assess whether in vivo treatment with idelalisib alters CLL cell sensitivity to therapy with antibodies or other kinase inhibitors
- To assess pharmacodynamic markers of PI3 kinase inhibition including AKT phosphorylation, production of T cell chemokines and response to CXCR 4/5
- To determine whether response or resistance correlates with genetic alterations in PIK3CA or PIK3CD or other genes
 - To assess the clonal dynamics of CLL in peripheral blood vs bone marrow, and during therapy with idelalisib.

Secondary Analysis:

The CR rate of combination therapy, ORR rate, and rate of nodal PR with lymphocytosis for idelalisib given alone for 2 months will be summarized as numbers and percentages. The Kaplan Meier method will be used to estimate the median progression free survival. The number and percent of patients who experience toxicities on combination therapy after at least one dose of treatment will also be summarized. Associations of clinical response rate and known prognostic factors will be assessed using Fisher's exact test.

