17. APPENDICES76

1. OBJECTIVES

1.1 Study Design

This study was designed to enroll 50 subjects with untreated chronic lymphocytic leukemia/small lymphocytic lymphoma (CLL/SLL) who meet IWCLL 2008 criteria for initiation of therapy will initiate single-agent idelalisib (GS1101), a PI3K delta specific inhibitor, daily for the first two months on study, and begin ofatumumab at the start of the 3rd month following a complete response evaluation. The duration of combination therapy will be 8 months. All subjects will receive 8 weekly doses of ofatumumab, following which they will undergo another response evaluation. They will then continue with idelalisib during their 4 monthly doses of ofatumumab. The final primary endpoint response evaluation will occur two months after completion of ofatumumab, at 10 months following start of therapy. Therapy with idelalisib will continue throughout the ofatumumab therapy and after, until development of progressive disease. Once participants are receiving single agent idelalisib therapy they will be seen in clinic every 2 months. After treatment is complete subjects will be followed every 3-6 months at the treating investigator's discretion until initiation of a new therapy or death. Subjects who do not complete cycle 2 are not considered evaluable for the study efficacy objectives and may be replaced. Their data will be included in all toxicity evaluations.

As of 3/11/2016, Gilead has observed an excess of infectious deaths in three trials, one in upfront CLL, and as a result the FDA and Gilead are discontinuing enrollment to upfront CLL trials as well as discontinuing the administration of idelalisib to patients previously enrolled on these trials. All patients on this trial however may receive ofatumumab as planned and continue to be followed per protocol. Correlative analyses will continue as previously planned.

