This document is confidential. Do not disclose or use except as authorized.

headache, nausea, diarrhea, or fatigue. No subject had tumor lysis syndrome. No overt pattern of myelosuppression was associated with idelalisib treatment. The data also did not suggest drug-related reductions in circulating CD4+ cells or serum Igs.

Among Grade 3-4 nonhematological adverse events, pneumonia/pneumonitis was observed most frequently, occurring in 24% of subjects with CLL. In most instances, these cases were considered bacterial in origin, based either on culture results or on response to conventional antibiotics. Subjects with CLL have occasionally been diagnosed with *Pneumocystis (carinii) jiroveci* pneumonia; the specific causal role of idelalisib has been difficult to elucidate because infection was sometimes present before starting idelalisib or the patients had other pre-existing risk factors. Such subjects were not receiving pneumocystis prophylaxis. The rate of pneumonia over time (0.045 events/subject/month) with idelalisib was not worse than the expected rate (0.06 events/patient/month) reported historically in comparable patients with recurrent CLL [9] .

Monitorable, reversible elevations of hepatic transaminases were observed in some subjects; ~5% of subjects with previously treated CLL had Grade 3-4 increases in serum ALT or AST. The onset of changes was time-dependent; among those with serum ALT/AST abnormalities, onset typically occurred 2 to 8 weeks after idelalisib initiation. In subjects with Grade 1-2 events, serum ALT/AST elevations resolved despite continued idelalisib dosing. In subjects with Grade 3-4 events, idelalisib was temporarily interrupted. Upon resolution of serum ALT/AST abnormalities, resumption of idelalisib at a reduced dose did not result in recurrence of serum transaminase increases in the majority (>70%) of subjects who were rechallenged. This pattern suggests an adaptation to the effect similar to that observed in dogs receiving idelalisib. Such an adaptive response is commonly observed with other drugs that induce transaminase elevations.

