This study activated for enrollment on June 16, 2014, and since then 15 patients have initiated on therapy. Among the first 8 patients to reach cycle 2, two patients developed grade 4 transaminitis. Transaminitis is a well-known side effect of idelalisib, and included as a black box warning in the FDA approved label. In these two cases the onset was rapid, and continued to increase after discontinuation of the drug. We have therefore previously amended the protocol to significantly increase the frequency of LFT monitoring during the high risk period. Additional observation has shown that this transaminitis appears to be inflammatory, based on the results of two liver biopsies showing a CD8 T cell infiltrate and the response of these patients to steroids and/or mycophenolate mofetil. We have developed an algorithm for the early initiation of steroids with the first signs of transaminitis which together with the frequent monitoring has resulted in predictable safety and much shorter drug interruptions. This amendment served to further refine that treatment algorithm.

An amendment was submitted in January 2015 to add correlative studies, in particular sequencing analysis of the clonal composition of CLL in PB vs BM at baseline, mid treatment and at final restaging. This analysis will still occur.

Rationale for Current Amendment 3/14/16

This amendment will take all patients off idelalisib, but allow them to receive ofatumumab and be followed per protocol assessments. All patients had discontinued idelalisib as of 3/11/16. They will undergo a full disease restaging with correlative samples within 30 days and be followed per protocol until further therapy, and after that just for overall survival.

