14.3 Reporting and Exclusions

14.3.1 Evaluation of toxicity. All participants who receive one dose of study therapy will be evaluable for toxicity from the time of their first treatment.

CONFIDENTIAL

This document is confidential. Do not disclose or use except as authorized.

14.3.2 Evaluation of response. All participants included in the study and who actually receive at least one dose of study therapy will be assessed for response to treatment, even if there are major protocol treatment deviations or if they are ineligible. Each participant should be assigned one of the following categories: 1) complete response, 2) partial response, 3) stable disease, 4) nodal response with lymphocytosis; 5) progressive disease, 6) early death from malignant disease, 7) early death from toxicity, 8) early death because of other cause, or 9) unknown (not assessable, insufficient data). By arbitrary convention, category 9 usually designates the "unknown" status of any type of data in a clinical database.

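### Toxicity is planned only as a crude percent on combination therapy, which does not give risk by time on idelalisib when exposure was cut off by 3/11/16

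*Combined protocol and SAP*

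**What the plan says.** The analysis sentence in Section 14.2 reads: "The number and percent of patients who experience toxicities on combination therapy after at least one dose of treatment will also be summarized". Section 14.3.1 sets the evaluable group: "All participants who receive one dose of study therapy will be evaluable for toxicity from the time of their first treatment". Section 14 contains no person-time rate, time to onset, cumulative incidence or exposure summary for toxicity. Section 14.1 was updated for closure at 27 patients, but 14.2 still describes toxicity in this one way.

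On exposure, Section 1.1 states the plan: "Therapy with idelalisib will continue throughout the ofatumumab therapy and after, until development of progressive disease". Section 2.5 gives the two dates that bound it. The start is "This study activated for enrollment on June 16, 2014" and the end is "All patients had discontinued idelalisib as of 3/11/16".

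Section 1.3 lists as an objective the safety of idelalisib in untreated participants as well as in combination with ofatumumab. Section 2.6(f) reports from this trial a rapid transaminitis and a colitis that comes later. Section 11.8 requires that "The presence and resolution of AEs and SAEs (with dates) should be documented on the appropriate case report form", and Section 12.1.2 has treatment forms submitted each cycle.

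**The concern.** A crude percent reads as a risk when patients have similar time at risk. Here an open-ended treatment was ended for everyone by one calendar date, so a late entrant has less time on idelalisib than an early one. In a percent over all treated patients both count fully in the denominator. For an early event such as transaminitis this matters little. For an event that tends to come later, some patients may never have reached the period when it occurs.

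There is also a gap in coverage. Read literally, the sentence summarises toxicities only in the combination period. Events in the two-month lead-in, and on idelalisib alone after ofatumumab, have no stated summary, although the objective in Section 1.3 includes them.

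Safety of this drug in untreated patients is probably the result of most interest after the withdrawal. A reader who takes the percent as the risk of a course of idelalisib could be misled.

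**Working it through.** **Plan's own figure.** The plan gives no numerical target, rate or precision for toxicity, so there is nothing on this point to reproduce.

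**Ceiling on exposure.** From 16 June 2014 to 11 March 2016 is 634 days; 634 / 30.4375 = 20.8 months. This is a maximum counted from activation, not an observed exposure. The documents give no entry dates beyond "This study activated for enrollment on June 16, 2014, and since then 15 patients have initiated on therapy", which stands under the heading on the 2014-2015 amendments. Section 5 provides for patients not yet at day 57 at the stop, but does not say whether there were any.

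**Illustration 1: constant hazard from month 4.** Assumptions: no events before month 4, constant hazard h afterwards, true 12-month risk 30%, uniform entry, no stops before 3/11/16.

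- h = -ln(1 - 0.30) / 8 = 0.0446 per month.
- A patient with exposure c months has an event within 12 months with probability 1 - exp(-h × max(min(c, 12) - 4, 0)).
- Between months 4 and 12 of exposure, the average of this is 1 - 0.30 / (8 × 0.0446) = 0.159.

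Entry up to the stop (c uniform on 0 to 20.8): a share 8/20.83 = 0.384 has c between 4 and 12, and 8.83/20.83 = 0.424 has c above 12. The crude figure is 0.384 × 0.159 + 0.424 × 0.30 = 0.188.

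Entry ending 3 months before the stop (c from 3 to 20.8): 8/17.83 × 0.159 + 8.83/17.83 × 0.30 = 0.220.

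Entry confined to the first 12 months (c from 8.8 to 20.8): the share with c below 12 is 3.17/12 = 0.264, with average risk 0.248. The crude figure is 0.264 × 0.248 + 0.736 × 0.30 = 0.286.

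| Entry pattern | Crude % within 12 months, true risk 30% | Same, true risk 40% | Crude % over all exposure, true 12-month risk 30% |
|---|---|---|---|
| Up to the stop | 18.8 | 25.3 | 24.0 |
| Ends 3 months before | 22.0 | 29.5 | 28.0 |
| First 12 months only | 28.6 | 38.3 | about 38 |

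The last column drops the 12-month cap. It falls below or above 30% according to accrual, so the crude percent has no fixed time horizon.

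**Illustration 2: a single late onset.** Take a 20% toxicity that always appears at one month of exposure. With exposure uniform from 0.5 to 20.8 months, the share reaching month 6 is 14.83/20.33 = 0.729, and month 12 is 8.83/20.33 = 0.434. The toxicity then shows as 14.6% or 8.7%. If all entry fell in the first 12 months it shows as 20.0% or 14.7%.

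**Illustration 3: same percent, different rates.** Suppose six of 27 patients each have one pneumonia: 6/27 = 22%. The mean exposures are chosen for the example.

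- Mean 5 months: 27 × 5 = 135 patient-months; 6/135 = 0.044 per patient-month, exact 95% Poisson interval 0.016 to 0.097.
- Mean 15 months: 27 × 15 = 405 patient-months; 6/405 = 0.015, interval 0.005 to 0.032.

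The percent is the same for rates that differ threefold. The intervals are wide and overlap, which is the precision to expect here.

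**The case against.** The strongest defence is that a crude adverse event table is ordinary descriptive reporting for a single-arm phase 2 trial. No inference rests on it, it states correctly what was observed, and the dates allow other summaries later. That stands as far as it goes: the percent is not wrong. It does not, however, give risk by time on drug, and no other summary is planned.

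A second defence is that the quoted sentence covers the combination period, planned as cycles 3 to 8, so open-ended exposure does not enter it and a patient who never reached ofatumumab would not dilute it. Read literally this is right. The arithmetic above therefore applies to a percent over all treated patients, the group that 14.3.1 makes evaluable. The literal reading also confirms that lead-in and post-induction toxicities have no stated summary.

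Two stronger readings are tempting. A reader might infer that late toxicities are understated as a matter of fact, with exposures running from weeks to 20.8 months. The documents do not support this. Neither end is a reported exposure, and with early accrual the shortfall nearly vanishes (28.6% against 30%). Patients may also have stopped earlier for progression or toxicity. Nor do the documents say that infection risk builds up with exposure: Section 2.2.4 gives deaths as crude percents (7.4% against 3.5%) without timing.

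A reader might also take 0.06 per patient-month as the plan's benchmark, because Section 2.2.2 states "The rate of pneumonia over time (0.045 events/subject/month) with idelalisib was not worse than the expected rate (0.06 events/patient/month" and Section 6.1.1 gives 0.04 over 360 patient-months. Section 14 makes no such comparison. The 0.06 is background from recurrent CLL, whereas this trial enrolled untreated patients and requires PCP and antiviral prophylaxis (Section 5.3.6).

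**Conclusion.** The concern holds in limited form. Section 14.2 plans only a crude number and percent, and only for the combination period, although idelalisib exposure was open-ended by plan and ended for all by 3/11/16. The percent is a valid description but not an estimate of risk by time on idelalisib.

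It may understate later-onset events. In Illustration 1 the shortfall against a true 12-month risk of 30% runs from about 1 to about 11 percentage points. Those figures rest on assumed uniform entry, an assumed hazard shape and no earlier stops. The actual effect cannot be computed, because the documents give no entry dates, exposures or event counts by time. Early events such as transaminitis should be little affected. This is an inexpensive improvement to the safety analysis, not a correction of a wrong number.

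**What to change.** In Section 14.2, keep the crude table and extend it to all toxicities from the first idelalisib dose, shown for lead-in, combination and post-induction periods. Add:

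1. A summary of idelalisib exposure duration and reasons for stopping.
2. For grade 3 or higher infection, pneumonitis, colitis/diarrhoea and transaminitis, events per patient-month with exact Poisson intervals.
3. For the same events, cumulative incidence from the first idelalisib dose, with death as a competing event.

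For the main analysis use the plan's own collection windows, including SAEs and deaths to 6 months after the last treatment (Sections 11.4.1 and 11.8). Count person-time over the same window as the events. Add an on-treatment-plus-30-days version as a sensitivity analysis only. Censoring there would drop delayed SAEs and deaths that the plan collects, and stops for toxicity may make it informative; the text should say so.

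Do not treat 0.06 per patient-month as a comparator. If it is cited, label it as background from recurrent CLL.

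The cost is a few lines of text and a little more programming, with no new data collection and no change to clinical management. The downside is wide intervals with 27 patients.
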